#### 4.4. Summary of Study Design

[figure not shown]
Study IBHD is a Phase 3b, multicenter, randomized, open-label, parallel clinical trial comparing U-500R administered by CSII (OmniPod U-500 system) to U-500R administered MDI in high-dose insulin-requiring subjects with T2DM who have inadequate glycemic control on high-dose non U-500R (>200 and ≤600 units per day) insulins (CSII or MDI) and/or U-500R insulin (MDI) with or without other insulins/AHAs. The trial design includes: 1-week screening period, 2-week lead-in period, and a 26-week treatment period (2 week transition to U-500R MDI administered TID, 12 weeks titration and 12 weeks maintenance U-500R CSII or MDI). As shown in the following recruitment plan ([Table IBHD.4.1](#)), approximately 320 subjects requiring high-dose insulin without use of GLP-1 receptor agonists or SGLT2 inhibitors (Group A) and approximately 64 to 96 additional subjects who are using GLP-1 receptor agonists or SGLT2 inhibitors (Group B) with or without other AHAs will be randomized based on a 1:1 ratio to 2 treatment arms. After Group A has been fully enrolled, Lilly may stop enrollment for Group B, even if the minimum recruitment goal for Group B has not been met. Approximately 240 (Group A) and 48 to 72 (Group B) subjects are expected to complete the 26-week treatment period (assuming a 25% dropout rate).

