**Figure IBHD.4.1. Illustration of study design for clinical protocol B5K-MC-IBHD.**

## 5. A Priori Statistical Methods

### 5.1. Sample Size Determination

Approximately 320 subjects requiring high-dose insulin without use of GLP-1 receptor agonists or SGLT2 inhibitors (Group A) and approximately 64 to 96 additional subjects with use of GLP-1 receptor agonists or SGLT2 inhibitors (Group B) will be randomized based on a 1:1 ratio to 2 treatment arms. Approximately 240 (Group A) and 48 to 72 (Group B) subjects are expected to complete the 26-week treatment period (assuming a 25% dropout rate).

The sample size was calculated based on the first primary objective for subjects without use of GLP-1 receptor agonists or SGLT2 inhibitors (Group A). The 240 completers will provide 80% statistical power to demonstrate the noninferiority (NIM is 0.4%; SD = 1.1%) of U-500R insulin CSII versus U-500R MDI in change in HbA1c at 26 weeks at 2-sided alpha = 0.05.

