The analysis approach for the rate of hypoglycemia is based on a negative binomial model with log link function, excluding post study treatment discontinuation data. The response variable is the hypoglycemic event count per visit per subject. For Group A, the model will include baseline hypoglycemia event rate for week interval (-2, 0] of the corresponding category of the dependent hypoglycemia variable standardized by 30 days as covariates, treatment (U-500R CSII, U-500R MDI), and the stratification factors (U-500R at entry versus other insulins, entry HbA1c  $\geq 8.5\%$  or  $< 8.5\%$ ) as fixed effects. For the analysis in Group A+B, the stratification factor (nonusers versus users of GLP-1 receptor agonists or SGLT2 inhibitors) will be added into the model. The logarithm of exposure days (standardized by 30 days) between visits will be used as the offset variable. In LSMeans statement, Observed Margin (OM) option will be added to specify weighting scheme for LSMean computation as determined by the input data set. The LSMean of hypoglycemia rate per 30-days by treatment for each week interval will be reported,

and the rate ratio between treatments will also be presented. Wilcoxon signed-rank test may be performed as sensitivity analysis.

The 1-year rate of documented symptomatic and severe hypoglycemia (with BG  $\leq$ 70 mg/dL) for every 2-hour interval (0:00-1:59, 2:00-3:59, 22:00-23:59) over the 26 week post-randomization period will be summarized. The rate of hypoglycemia will also be analyzed using a negative binomial model. The response variable is the hypoglycemic event count per 2-hour interval per subject. The analysis approach will be similar to the hypoglycemia rate analysis approach above for Group A and Group A+B.

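### The optional sensitivity test for the hypoglycemia rate is a Wilcoxon signed-rank test, which needs paired data and so cannot check a comparison of two independent arms

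*SAP*

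**What the plan says.** Rate and incidence of hypoglycemia form one of the other secondary objectives, stated as a comparison of CSII with MDI in Group A and in Group A+B (SAP Section 4.2.2).

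For the rate, SAP Section 5.13.2.1 states: "The analysis approach for the rate of hypoglycemia is based on a negative binomial model with log link function". On the data it says: "The response variable is the hypoglycemic event count per visit per subject". Treatment and the stratification factors are fixed effects, the lead-in event rate is a covariate, log exposure is the offset, and data after treatment discontinuation are excluded. The output is the rate by treatment for each week interval, "and the rate ratio between treatments will also be presented. Wilcoxon signed-rank test may be performed as sensitivity analysis".

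On design, SAP Section 4.4 says: "Study IBHD is a Phase 3b, multicenter, randomized, open-label, parallel clinical trial comparing U-500R administered by CSII". Section 5.1 adds that subjects "will be randomized based on a 1:1 ratio to 2 treatment arms".

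Protocol Section 12.2.10.1 gives only negative binomial regression for the rate. Neither document names a rank-sum test.

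**The concern.** The sentence follows directly on the between-treatment rate ratio, so the natural reading is that the signed-rank test is meant to check that ratio. It cannot, because it needs a difference for each pair or each subject and each subject here belongs to one arm only. No other sensitivity analysis of the rate model is named in that section.

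What is at stake is the use of the check, not the main result. Whoever programs the analysis would have to run a test that answers another question, pair unrelated subjects, or substitute a different test without a prespecified basis. The analysis by 2-hour intervals is to follow a similar approach and may inherit the same wording.

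**Working it through.** **1. What the plan's own figures give.** No power or precision is stated for the hypoglycemia rate or its sensitivity test, so there is no plan figure to reproduce for this point. The only sample-size figure is for HbA1c noninferiority, and it does reproduce:

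- n per arm = 2(1.960 + 0.842)² × 1.1² / 0.4² = 118.7, so 119 per arm and 238 in total, against 240 stated.
- Power with 120 per arm is 80.4%, against 80% stated.
- 240 / (1 − 0.25) = 320 randomized, or 160 per arm in Group A. That arm size is used below.

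**2. The test set against the design.**

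- The signed-rank test ranks |dᵢ|, where dᵢ is a within-pair or within-subject difference, and tests whether the dᵢ are centered on zero.
- The rate ratio compares the CSII rate with the MDI rate, in different subjects.
- The SAP defines no pairs, no within-subject difference and no within-arm hypothesis for this test.

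Two uses remain. The first is dᵢ = on-treatment rate minus lead-in rate within an arm. This tests change over time, which includes the move of all subjects to U-500R MDI after randomization. The second is dᵢ = CSII subject minus MDI subject in row order. The result then depends on how the file is sorted, and with unequal arms (160 and 157 were tried) the test cannot be computed.

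**3. Illustration only.** The documents give no hypoglycemia rates. The event rates, frailty variance and rise over time below are assumptions, and two scenarios are shown as a limited range. Both use 160 per arm, a 14-day lead-in, a 1.5-fold rise on treatment common to both arms, and 2000 simulated trials.

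| Assumed scenario | True CSII/MDI ratio | Signed-rank on change from lead-in, p<0.05 | Rank-sum between arms, p<0.05 |
|---|---|---|---|
| Lead-in 1.0 per 30 days, gamma frailty variance 1 | 1.0 | 99.7% (within arm) | 4.8% |
| Lead-in 2.0 per 30 days, gamma shape 0.7 (variance 1/0.7 = 1.43) | 1.0 | 100% (CSII alone, or arms pooled) | 5.0% |
| Same as the row above | 1.5 | 100% (CSII alone, or arms pooled) | 70% |

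In the second scenario the signed-rank result is the same whether the arms are equal or differ 1.5-fold, so there it says nothing about the ratio. The two test columns address different null hypotheses; they are not rival error rates for one question.

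For arbitrary cross-arm pairing, two simulated data sets with a true arm difference were each re-paired 1000 times. The signed-rank p-value ran from 0.0002 to 0.037 in one (rank-sum 0.008) and from 0.0003 to 0.080 in the other (rank-sum 0.007). In the second set 99.8% of pairings still gave p<0.05. The p-value is arbitrary, but in these examples it seldom crossed the threshold.

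**The case against.** Four points can fairly be made on the other side.

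- **The test is optional and minor.** The SAP says only that it may be performed. No planned estimate, interval, sample size or decision rule rests on it, and the model already provides for overdispersion, exposure, the lead-in rate and the stratification factors. This stands and limits the weight of the point. It does not make the named test suitable.
- **A within-arm use would be legitimate.** The SAP collects a lead-in rate, and Section 5.2 reports within-treatment p-values for change from baseline. However, Section 5.2 says this in the context of continuous measures, and Section 5.13.2.1 states no such purpose. Even on that reading the test would not check the rate ratio.
- **A reader might infer that the test would produce false positives when the arms are identical.** The material does not support that. In the simulations the rate really does rise in both arms, and the signed-rank test correctly detects it. The fault is that it answers another question.
- **A reader might also infer that the hypoglycemia comparison itself is unsound.** The documents do not support that either. The negative binomial model is a between-arm analysis, and its rate ratio does not depend on this test.

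The wording is probably a slip for the rank-sum test. Section 5.13.1 does use a two-sample test to compare exposure between the arms.

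**Conclusion.** The point holds as a specific, limited correction. As written, the optional signed-rank test cannot check the CSII/MDI hypoglycemia rate ratio, because the arms are independent and no pairing is defined. This follows from the definition of the test and the parallel design, and needs no assumed event rate. The simulations only illustrate it, and their size should not be read as harm expected in this trial.

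The consequence is confined to a sensitivity analysis of an other secondary safety objective, outside H1 to H10. It is worth correcting because the sentence is wrong as it stands and a precise replacement is at hand.

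**What to change.** In SAP Section 5.13.2.1, replace the signed-rank test with the Wilcoxon rank-sum test on each subject's exposure-adjusted event rate in the interval, one value per subject, excluding data after treatment discontinuation as the model does. The van Elteren version, stratified by the randomization factors, is an option and not a necessity. State whether the same check applies to the 2-hour-interval analysis. If a within-arm comparison with lead-in was intended, say that and do not present it as a sensitivity analysis of the rate ratio.

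The cost is a line or two of SAP text and a small analytic price. The rank test drops the lead-in rate as a covariate and gives a rate from short exposure the same weight as one from full exposure. It will be heavily tied for rare events such as severe hypoglycemia. It also checks direction and significance without estimating the ratio, so it should stay a supplement to the negative binomial model.

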### **5.13.3. Treatment Emergent Adverse Events and Serious Adverse Events**

Adverse events will be summarized as TEAEs (defined as events that are newly reported after randomization Visit 4 or reported to worsen in severity from randomization Visit 4) for ARS by treatment. The frequency and proportion of subjects experiencing at least 1 of each reported TEAE will be summarized by System Organ Class (SOC), Preferred Term (PT), and treatment group. Events will be ordered by decreasing frequency within SOC. The frequency and proportion comparisons will be analyzed using Fisher's exact test. The frequency and proportion of subjects experiencing at least 1 of each reported TEAE that are assessed as possibly related to the study drug, device, procedures will also be summarized, separately.

All SAEs (including severe hypoglycemic events) will be listed by subject including SOC, Medical Dictionary for Regulatory Activities (MedDRA) PT, severity, and relationship to the study disease, drug, device, or procedure for all subjects. The listing will contain data after the subjects discontinue the study treatment.

If a sufficient number of SAEs are reported, then a frequency and proportion summary, similar to the summary for TEAEs, will be included for the ARS.

Discontinuations due to AEs and SAEs will be listed separately, by subject (including specific AE and SAE information and whether they discontinue only the study treatment or study treatment and the study), and summarized (if a sufficient number of events are reported) by SOC, PT, and treatment group.

### **5.13.4. Body Weight**

The body weight actual value and CFBL based on actual value at visits will be analyzed by MMRM models similar to that which will be used in the primary analysis for the ARS population. An ANCOVA model will also be used as a sensitivity analysis. A scatter plot that includes a regression line of LOCF weight CFBL by LOCF HbA1c CFBL will be presented.

For Group A, the MMRM model will include the following fixed effects: treatment (U-500R CSII, U-500R MDI), weeks on treatment, the interaction between treatment and weeks, and the stratification factors (U-500R at entry versus other insulins, entry HbA1c  $\geq$ 8.5% or  $<$ 8.5%). The model will also include the corresponding baseline of the response variable. The ANCOVA model will include the following fixed effects: treatment (U-500R CSII, U-500R MDI), the

stratification factors (U-500R at entry versus other insulins, entry HbA1c  $\geq 8.5\%$  or  $< 8.5\%$ ), and the baseline weight as covariate.

For Group A+B, the same MMRM model and ANCOVA models in Group A above will be used with the addition of the stratification factor (nonusers versus users of GLP-1 receptor agonists or SGLT2 inhibitors).

### 5.13.5. Vital Signs

Systolic blood pressure, diastolic blood pressure, and pulse rate will be summarized at each scheduled visit including baseline for the ARS in Group A+B. Additionally, CFBL for all postrandomization visits will be summarized. The CFBL and actual value at visits will be analyzed using a MMRM model with the following fixed effects: treatment (U-500R CSII, U-500R MDI), weeks on treatment, the interaction between treatment and weeks, and the stratification factors (U-500R at entry versus other insulins, entry HbA1c  $\geq 8.5\%$  or  $< 8.5\%$ , nonusers versus users of GLP-1 receptor agonists or SGLT2 inhibitors). The model will also include the corresponding baseline measures as a covariate. The actual value and CFBL based on LOCF endpoint will be analyzed using ANCOVA model, as a sensitivity analysis. The ANCOVA model will include the same fixed effects in the MMRM model but without the terms involving weeks.

### 5.13.6. Laboratory Measures

As applicable per protocol, measures within the following panels will be summarized at Screening (Visit 1), Visit 4 (Week 0), Visit 13 (Week 14), and Visit 17 (Week 26) or endpoint (LOCF):

- chemistry (creatinine, uric acid)
- c-peptide
- eGFR
- lipids (total cholesterol, calculated low-density lipoprotein cholesterol [LDL-C], high-density lipoprotein cholesterol [HDL-C], triglycerides [TG], and free fatty acids [FFAs])
- liver test panel (alanine aminotransferase [ALT], aspartate aminotransferase [AST], gamma-glutamyl transferase, alkaline phosphatase)

Treatment-emergent high, low, and abnormal values will be summarized for each lab measure listed above. A treatment-emergent **high value** is defined as a value that was normal or low at baseline and subsequently found to be above the normal range at any post-baseline visit. A treatment-emergent **low value** is defined as a value that was normal or high at baseline and subsequently found to be below the normal range at any post-baseline visit. A treatment-emergent **abnormal value** is defined as a value that was normal at baseline and subsequently found to be abnormal at any post-baseline visit; however, for ALT/serum glutamic pyruvic transaminase (SGPT) or AST/serum glutamic oxaloacetic transaminase (SGOT)  $\geq 2.5X$  upper limit of normal (ULN) will be used as the abnormal threshold. The proportion comparisons between 2 treatment groups will be analyzed using Fisher's exact test.

Actual value, percentage CFBL in lipids panel (total cholesterol, calculated LDL-C, HDL-C, TG, FFAs), and CFBL in other measures will be summarized and analyzed. If only one post-baseline measurement is scheduled, then an ANCOVA model will be used; if more than one post-baseline measurement is scheduled, then an MMRM model will be used. The MMRM model will include the following fixed effects: treatment (U-500R CSII, U-500R MDI), weeks on treatment, the interaction between treatment and weeks, and the stratification factors (U-500R at entry versus other insulins, entry HbA1c  $\geq 8.5\%$  or  $< 8.5\%$ , nonusers versus users of GLP-1 receptor agonists or SGLT2 inhibitors). The model will also include the corresponding baseline measures as a covariate. The ANCOVA model will include the same fixed effects in the MMRM model but without the terms involving weeks.

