TEAEs and serious adverse events (SAEs): Adverse events will be listed by subject, system organ class, preferred term, severity, and relationship to the study disease, drug, device, or procedure. Adverse events will be summarized as TEAEs during treatment period (defined as events that are newly reported after randomization Visit 4 or reported to be worsened in severity from randomization Visit 4) for ARS by treatment and visit. The frequency and proportion of subjects experiencing at least 1 of each reported TEAE will be summarized for treatment period. The frequency and proportion comparisons will be analyzed using Fisher's exact test or Pearson's chi-square test, as appropriate. The frequency and proportion of subjects experiencing at least 1 of each reported TEAE that are assessed as possibly related to the study disease, drug, device, or procedures will also be summarized. All SAEs (including severe hypoglycemic events) will be listed by subject with similar information as the AE listing. If a sufficient number of SAEs are reported, then a frequency and proportion summary, similar to the summary for TEAEs, will be included for the ARS.

Vital Signs: Systolic and diastolic blood pressures and pulse will be summarized by visit and for endpoints (LOCF). Change from baseline to the last visit of each period for actual endpoint and endpoint (LOCF) will be summarized.

Study Treatment Exposure: Exposure to each treatment will be calculated for each subject and summarized by treatment. Total subject-years will be included in the summaries.

Laboratory Measures (chemistry, hematology, lipids): Treatment-emergent high, low, and abnormal values will be summarized for each lab measure.

Further details of analyses will be provided in the SAP.

Patient Reported Outcome Measures: As an exploratory objective, the TRIM-D and TRIM-DD measures will be used to compare the change in diabetes treatment and diabetes treatment device on patient's functioning, well-being and quality-of-life outcomes from baseline to the 26-week values between treatment groups. These analyses will be performed on the ARS using a MMRM model (similar to the primary/secondary analyses). Summaries of the continuous variables will include sample size, mean, SD, median, minimum, maximum, LS mean and standard error (SE) of LS mean.

3. Table of Contents

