10.4.5. Safety Monitoring

The Lilly CRP or CRS will monitor safety data throughout the course of the study.

Lilly will review SAEs within timeframes mandated by company procedures. The Lilly CRP/CRS will, as is appropriate, consult with the functionally independent Global Patient Safety therapeutic area physician or clinical scientist, and periodically review:

- Trends in safety data
- Laboratory analytes
- AEs
- Product complaints

If a study subject experiences elevated ALT or AST $\geq 3X$ ULN, elevated total bilirubin $\geq 2X$ ULN, or alkaline phosphatase $\geq 2X$ ULN, clinical and laboratory monitoring should be initiated by the investigator. Details for hepatic monitoring depend upon the severity and persistence of observed laboratory test abnormalities. To ensure subject safety and comply with regulatory guidance, the investigator is to consult with the Lilly designated medical monitor regarding collection of specific recommended clinical information and follow-up laboratory tests.

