12.2.10.6. Laboratory Measures

As applicable per protocol, measures within the following panels will be summarized at Screening (Visit 1), Visit 4 (Week 0), Visit 13 (Week 14), and Visit 17 (Week 26) or endpoint (LOCF):

- Chemistry
- Hematology
- Lipids

Treatment-emergent high, low, and abnormal values will be summarized for each lab measure.

A treatment-emergent **high value** is defined as a value that was normal or low at baseline and subsequently found to be above the normal range at any post-baseline visit. A treatment-emergent **low value** is defined as a value that was normal or high at baseline and subsequently found to be below the normal range at any post-baseline visit. A treatment-emergent **abnormal value** is defined as a value that was normal at baseline and subsequently found to be abnormal at any post-baseline visit.

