Attachment 1. Protocol IBHD Study Schedule

Study Schedule, Protocol B5K-MC-IBHD

Perform procedure as indicated.

↓ Visit 6: CSII Treatment Arm Begins

	S	Lead- In		R	Transition		Treatment Period										ET ^a	
Visit Number	1	2	3	4	5	6	7	8	9	10	11	12	13	14	15	16	17	
Week of Study (week prior to visit)	-3	-2	-1	0	1	2	3	4	6	8	10	12	14	17	20	23	26	
Allowable Range (± d=days, w=weeks)	-	1w	3d	1w	3d	3d	3d	3d	3d	3d	3d	3d	3d	3d	3d	3d	1w	
Telephone (T) or Office (O) Visit	O	O	T	O	O	O	O	T	T	O	T	T	O	T	O	T	O	
Informed consent	X																	
Confirm eligibility	X			X ^b														
Demographic data	X																	
Randomization				X														
IWRS	X	X	X	X	X	X	X	X	X	X	X	X	X	X	X	X	X	X
Laboratory Assessments^c																		
Subjects fast prior to visit				X									X				X	X
Clinical chemistry/hematology	X			X									X				X	X
Estimated glomerular filtration rate (eGFR)	X			X									X				X	X
Lipid panel				X									X				X	X
Urinalysis	X																X	X
Pregnancy test ^d	X																	
HbA1c	X			X						X			X		X		X	X
Fasting plasma glucose				X									X				X	X
C-peptide				X													X	X
Pharmacogenetic sample for storage				X														
Nonpharmacogenetic biomarkers sample storage (plasma, serum, urine)	X			X						X			X		X		X	X
Clinical Assessments																		
ECG	X																	
Medical history	X																	
Preexisting conditions	X																	
Physical examination	X																	
Concomitant medications	X	X	X	X	X	X	X	X	X	X	X	X	X	X	X	X	X	X

↓ Visit 6: CSII Treatment Arm Begins

	S	Lead- In			R	Transition		Treatment Period										ET ^a	
Visit Number	1	2	3	4	5	6	7	8	9	10	11	12	13	14	15	16	17		
Week of Study (week prior to visit)	-3	-2	-1	0	1	2	3	4	6	8	10	12	14	17	20	23	26		
Allowable Range (± d=days, w=weeks)	-	1w	3d	1w	3d	3d	3d	3d	3d	3d	3d	3d	3d	3d	3d	3d	1w		
Telephone (T) or Office (O) Visit	O	O	T	O	O	O	O	T	T	O	T	T	O	T	O	T	O		
Clinical Assessments, Cont.																			
Assess/record BG and hypoglycemic events ^e		X	X	X	X	X	X	X	X	X	X	X	X	X	X	X	X	X	
Adverse Events ^c		X	X	X	X	X	X	X	X	X	X	X	X	X	X	X	X	X	
Vital signs	X	X		X	X	X	X			X			X		X		X	X	
Weight	X	X		X	X	X	X			X			X		X		X	X	
Height	X																		
Training on 7-point SMBG profiles		X																	
Subject records 7-point SMBG profiles ^f				X									X				X		
Health Outcomes Questionnaires																			
TRIM-D				X ^g										X				X	X
TRIM-DD				X ^g										X				X	X
Pump Specific Endpoint Assessment																			

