Attachment 2. Protocol IBHD Clinical Laboratory Tests

Clinical Laboratory Tests^a

Hematology	Clinical Chemistry	Urinalysis
Hemoglobin	BUN	Bilirubin
Hematocrit	Creatinine	Blood
MCH	Uric acid	Glucose
MCHC	LDH	Ketones
MCV	Albumin	Urine leukocyte esterase
Platelets	Total Protein	Nitrite
Erythrocyte count (RBC)	Calcium	pH
RBC Morphology	Magnesium	Protein
Leukocytes (WBC)	Chloride	Specific gravity
WBC Differential	Potassium	Urobilinogen
Neutrophils, segmented	Sodium	^b Microscopic
Lymphocytes	Phosphorus	
Monocytes	Bicarbonate	eGFR (MDRD equation)
Eosinophils	CK	
Basophils	Total bilirubin	
	Direct bilirubin	
HbA1c	Alkaline phosphatase	
Glucose, fasting plasma	Alanine aminotransferase (ALT)	
C-peptide	Aspartate aminotransferase (AST)	
	Gamma-Glutamyl Transferase (GGT)	
CDC Lipid Panel	Pregnancy Test (females only)	
Cholesterol		
Triglycerides		
HDL		
LDL (calculated)		
FFA		
		Storage Samples
		Non-PGx Biomarkers:
		Urine, Serum, Plasma
		PGx: DNA Whole Blood

Abbreviations: BUN = blood urea nitrogen; CDC = Centers for Disease Control and Prevention; CK = creatine kinase; DNA = deoxyribonucleic acid; FFA= free fatty acids; HbA1c = hemoglobin A1c; HDL = high density lipoprotein; LDH = lactic acid dehydrogenase; LDL = low-density lipoprotein; MCH = mean cell hemoglobin; MCHC = mean cell hemoglobin concentration; MCV = mean corpuscular volume; PGx = pharmacogenetics; RBC = red blood cells; WBC = white blood cells; eGFR = estimated glomerular filtration rate; MDRD = Modification of Diet in Renal Disease.

^a Assayed by Lilly-designated central laboratory.

^b Microscopic evaluation if any listed urinalysis analyte is positive.

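### SAP 5.13.6 leaves out the whole hematology panel and 14 of 20 chemistry analytes that the protocol commits to summarize, and gives no reason

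*SAP*

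**What the plan says.** The protocol states the commitment twice. The synopsis reads: "Laboratory Measures (chemistry, hematology, lipids): Treatment-emergent high, low, and abnormal values will be summarized for each lab measure". Section 12.2.10.6 names the same three panels, to be summarized at Visits 1, 4, 13 and 17 or at the LOCF endpoint, and adds: "Treatment-emergent high, low, and abnormal values will be summarized for each lab measure".

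Attachment 2 sets out what the central laboratory measures. Its chemistry column includes potassium, total bilirubin and "Direct bilirubin"; its hematology column starts with hemoglobin. In Attachment 1 the row "Clinical chemistry/hematology" is marked at Visits 1, 4, 13, 17 and early termination.

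SAP 5.13.6 opens with almost the same lead-in as the protocol but changes the list beneath it. The chemistry bullet is reduced to "chemistry (creatinine, uric acid", two analytes. C-peptide and eGFR are added, the lipids stay, and a separate liver bullet gives ALT, AST, GGT and alkaline phosphatase. There is no hematology bullet. The SAP then writes: "Treatment-emergent high, low, and abnormal values will be summarized for each lab measure listed above". The last two words of that sentence tie the tables to the shortened list.

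**The concern.** The two documents describe different laboratory analyses, and programmers will work from the SAP. If it is followed as written, the report will have no by-arm summary or treatment-emergent table for any blood count, for any electrolyte, or for bilirubin.

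This is an open-label comparison of two ways of giving high-dose insulin, one through an investigational pump. Laboratory tests are a named safety criterion in the protocol. A shift in one of the omitted analytes that did not lead to a diagnosis would probably not reach the adverse event tables, so the planned laboratory table is where a difference between arms would be seen. What is at stake is the completeness of the promised safety comparison. The primary HbA1c result is not at stake.

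**Working it through.** The check is a count of Attachment 2 against the list in SAP 5.13.6. No sample-size, power or alpha figure enters, and the plan states no figure to reproduce.

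**Rules for the count.** Only the three panels named in protocol 12.2.10.6 are counted. The SAP is credited for its separate liver bullet as well as its chemistry bullet. The white-cell differential counts as its five components. HbA1c is printed below the hematology column but is the efficacy measure, so it is not counted as hematology. C-peptide and eGFR lie outside the three panels and are not counted on either side.

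| Panel | Items in Attachment 2 | Named in SAP 5.13.6 | Not named |
|---|---|---|---|
| Chemistry | 20 | 6 | 20 − 6 = 14 |
| Hematology | 14 | 0 | 14 − 0 = 14 |
| Lipids | 5 | 5 | 5 − 5 = 0 |
| Total | 39 | 11 | 39 − 11 = 28 |

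**Chemistry kept (6):** creatinine and uric acid from the chemistry bullet; ALT, AST, GGT and alkaline phosphatase from the liver bullet. Without the liver bullet the figure would be 2 of 20.

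**Chemistry omitted (14):**
- electrolytes and minerals: sodium, potassium, chloride, bicarbonate, calcium, magnesium, phosphorus (7)
- bilirubin: total and direct (2)
- proteins: albumin, total protein (2)
- enzymes: LDH, CK (2)
- BUN (1)

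Check: 7 + 2 + 2 + 2 + 1 = 14.

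**Hematology omitted (14):**
- red-cell items: hemoglobin, hematocrit, erythrocyte count, MCV, MCH, MCHC, red-cell morphology (7)
- platelets (1)
- leukocytes (1)
- differential counts (5)

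Check: 7 + 1 + 1 + 5 = 14.

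**Is the SAP list closed?** Where the SAP means a list to be open, it says so: the baseline characteristics in 5.5, the deviation table in 5.8 and the rescue listing in 5.14 all carry such wording. Section 5.13.6 carries none. The phrase in its lead-in that refers back to the protocol does not reopen the list, because the parentheses and the restriction to measures already named decide what is tabulated.

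**The case against.** The best defence is that the SAP is where analysis detail belongs. The protocol defers further safety detail to it, and 12.2.10.6 speaks of measures within panels, as applicable, so some selection of chemistry analytes is arguable. Protocol 12.2.1 and SAP 5.2 also let non-principal changes be justified in the study report. The data are collected and watched in any case: investigators document their review of each laboratory report (10.5.1), clinically significant findings that lead to a diagnosis are reported (10.4.1), the sponsor's physician reviews laboratory analytes (10.4.5), and a data monitoring committee works under a charter not available here.

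Part of this stands. The omission of single chemistry analytes is less clear-cut than the loss of a panel that the protocol names. But the protocol's promise covers each measure, deferring detail does not remove a panel, and a later note in the study report does not supply the tables. Review of individual subjects is not a comparison between arms.

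A reader might also infer four stronger things, and the documents support none of them.

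- *Laboratory safety would not be compared between arms at all.* SAP 5.13.6 compares creatinine, uric acid, C-peptide, eGFR, lipids and four liver enzymes, with Fisher's exact test for proportions and MMRM or ANCOVA for values.
- *The hepatic monitoring levels in protocol 10.4.5 cannot be tabulated.* Those levels are a rule for the individual subject, after which "clinical and laboratory monitoring should be initiated by the investigator". The protocol promises no counts by arm. The SAP's 2.5X ULN cut for abnormal ALT or AST equals the level in exclusion criterion [9]. Because 2.5 is below 3, it includes every value at or above 3X ULN in subjects normal at baseline. Alkaline phosphatase is kept. What remains is that bilirubin has no planned table.
- *Untabulated hemoglobin changes could distort the HbA1c comparison.* Protocol 8.3.2 stops study treatment if the conditions in exclusion [13] (transfusion, severe blood loss, hemolytic anemia and similar) develop after enrollment. SAP Table IBHD.5.1, deviation 21, excludes subjects who had them at entry from the per-protocol set. Both arms receive the same insulin, and neither document suggests that hemoglobin would move differently by arm.
- *The SAP's revision history conceals the reduction.* It describes changes from SAP version 1, which is not available. If version 1 had the same list, there was nothing to record.

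**Conclusion.** The conflict is real. Of 39 items in the three panels that the protocol commits to summarize, the SAP names 11 and omits 28: all 14 hematology items and 14 of 20 chemistry analytes, including every electrolyte and both bilirubin measures. SAP 5.13.6 gives no reason.

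This rests on two readings: that Attachment 2 defines the content of the panels named in 12.2.10.6, and that the SAP list is closed. If the first were relaxed to allow selection within a panel, the chemistry count would be open to argument, but the missing hematology panel would not.

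The point should be corrected before the final tables are produced. It touches no hypothesis, endpoint, sample size or monitoring action.

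**What to change.** In SAP 5.13.6, add the hematology panel and the omitted chemistry analytes, at least the electrolytes and total and direct bilirubin, to the by-arm summaries and the treatment-emergent high, low and abnormal tables. Use the central-laboratory results already scheduled at Visits 1, 4, 13 and 17. Red-cell morphology has no high or low direction, so it needs only an abnormal category. If any analyte is left out on purpose, name it in the SAP, give the reason, and reconcile the text with protocol 12.2.10.6.

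Counts by arm at the monitoring levels in protocol 10.4.5 would be a useful optional addition, but the protocol does not commit to them.

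The cost is SAP wording, standard programming and more table pages. No new samples or visits are needed.
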